- Each subject will be made aware that his or her records will remain confidential, but that the FDA and the IRB has the right to inspect his or her records.
- Each subject will be told that his or her participation in the clinical study is voluntary, without force or influence from the investigator or sponsor.
- Each subject will be given the name and method of contacting the appropriate person(s) to answer his or her questions about the research and in the event of a research-related injury.

CASE REPORT FORMS

The case report forms that will be used to collect the data from each subject in this clinical study can be found in **Appendix**

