- APPENDIX B: PI INSTRUCTIONS FOR VAS MEASUREMENTS
- APPENDIX C: NPSI & RELATED JOURNAL ARTICLES
- APPENDIX D: CASE REPORT FORMS

STUDY INFORMATION

SPONSOR

Erchonia Corporation
[name]
[name]
Contact: [name], President
[contact]
E-mail: [contact]

REGULATORY CONSULTANT

Regulatory Insight, Inc., Denver Office
[name]
[name]
Contact: [name], Principal Consultant
[contact]
E-mail: [contact]

CLINICAL CONSULTANT

Regulatory Insight, Inc., Nashville Office
[name]
[name]
Contact: [name], Clinical Consultant
[contact]
E-mail: [contact]

MONITOR

Erchonia Corporation
[name]
[name]
Contact: [name]
[contact]
E-mail: [contact]

PRINCIPAL CLINICAL INVESTIGATORS AND TEST SITES

- [name], DPM, MS
Hialeah Hospital Medical Plaza
[name]
[name]
[contact]
e-mail: [contact]
IRB Study Number: 1251019

- [name], DPM
Pensacola Podiatry, P.A.
[name]
[name]
[contact]
e-mail: [contact]

INSTITUTIONAL REVIEW BOARD

Western Institutional Review Board® (WIRB®)

[name]

[name]

[contact]

e-mail: [contact]

IRB Tracking No. : 20150254

PURPOSE OF STUDY

The purpose of this clinical study is to determine the effectiveness of the Erchonia® FX-635™, manufactured by Erchonia Corporation (the Company), in providing relief of foot pain in individuals with chronic painful diabetic peripheral neuropathy.

INDICATION FOR USE

The indication (claim) being sought through support of the results of this clinical study is: "The Erchonia® FX-635™ is indicated for adjunctive use in providing relief of chronic pain arising from diabetic peripheral neuropathy."

It is intended that the results of this clinical study be used to support a 510(k) submission to FDA for clearance to market the device for the intended indication.

EXPECTED RESULTS

Following completion of the study procedure protocol with the Erchonia® FX-635™ relative to baseline, it is anticipated that significantly more subjects in the test group than in the placebo group will show a 30% or greater reduction in self-reported VAS pain rating in the feet.

RESOURCES

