The 'fake' (placebo) laser device will appear to the subject to be an active device but will not produce any therapeutic light output. The placebo laser device is designed to have the same physical appearance as the actual (active test) laser device, including the appearance of any **visible** light output. Therefore, both the test and control devices emit light when activated that is indistinguishable to the subject. As the laser light does not put out any notable degree of heat or noise, these are not distinguishing factors for subjects between the active and control devices.

Apart from the distinction of whether the subject receives the study procedures with the actual or the fake laser device, all subjects and investigative parties will adhere to all phases of the entire protocol design.

DOUBLE BLIND DESIGN

This clinical study will be a double-blind design, such that neither the subject nor the investigator will be aware of whether a subject is receiving the study procedures with the active (test procedure group assignment) or the 'fake' (placebo procedure group assignment) Erchonia® FX-635™ until after the study is completed.

Maintenance of study double-blind throughout the entire course of the study will be achieved through the following means:

- 1) Each subject will be randomly assigned to Procedure Group A or to Procedure Group B by the independent study Monitor. Subjects assigned to Procedure Group A will be treated with the Erchonia® FX-635™ A and subjects assigned to Procedure Group B will be treated with Erchonia® FX-635™ B. Only the study Sponsor will know which label ('A' or 'B') corresponds to the actual (test) FX-635™ device and which label corresponds to the 'fake' device until the final study data analysis is complete. The Sponsor will ensure that this information is stored and maintained confidentially at the Sponsor's work site. This knowledge will not be shared with the investigators, the subjects, or the study Monitor until the final data analysis is complete.

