- 2) The fake (placebo) Erchonia® FX-635™ is designed to have the same physical appearance as the actual Erchonia® FX-635™, including the appearance of any **visible** light output, with the placebo device employing a 635 nm LED rather than a 635 nm laser diode in the active device. Therefore, both the test and sham devices emit light when activated that is indistinguishable to both the subject and to the investigator. As the laser light does not put out any notable degree of heat or noise, these are not distinguishing factors for subjects between the two groups.
- 3) There will be two independent investigators interacting with subjects: (i) *administration investigator*: who will be responsible for administering the study treatments; (ii) *assessment investigator*: who will be responsible for recording the study outcome measures. Only the administration investigator will be aware of whether a subject is assigned to Procedure Group A or B, although he or she will not be made aware of whether A or B corresponds to the true or fake laser. Neither the assessment investigator nor the subject will be aware of the subject's A/B Group assignment. In this way, the assessment investigator will not be able to form an association between A/B Procedure Group and active/sham device over the course of the study if a treatment effect is observed.
- 4) During the laser procedures, both the subject and the administration investigator will wear safety glasses that filter out the laser light spectrum.

RANDOMIZATION

Subject allocation to procedure group will be via variable block randomization with varying block sizes of two, four and six used at random to minimize the likelihood of predicting the next procedure group assignment. In addition, randomization will be stratified by test site.

Randomization will be attained using computer generation sequence methodology, insuring that the randomization methodology and the generated allocation sequence is concealed from the investigator and subjects.

Concealment will be insured as follows:

- (ii) Each computer-generated randomization sequence is unique and will therefore not be able to be replicated.
- (iii) Randomization will occur to either 'Procedure Group A' or to 'Procedure Group B' rather than to a test or placebo group, and only the Investigational Device Engineer will know which assignment (A or B) corresponds to the active device and which

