corresponds to the fake device. The Engineer will not reveal this information to any source (investigators, subjects, CRO, or Sponsor) until the final study data analysis is complete and the Post-Study Open-Label phase begins.

Once a subject has signed the informed consent form, the Principal Investigator will contact the Sponsor (via email or phone) who will act as the central source for providing sequential subject procedure group assignment.

SUBJECTS

Subject Sample

Subjects will be males and females aged 18 years or older who have diagnosed diabetic peripheral neuropathy with pain persisting over at least the past three months.

Sample size

There will be 64 qualified subjects enrolled in this clinical study:

32 subjects in the active procedure group
32 subjects in the control procedure group

Rationale for sample size

Based on the following parameters established for the purposes of assessing efficacy of the Erchonia® FX-635™ in this clinical study ...:

- Individual subject success criteria defined as a 30% or greater reduction in self-reported Degree of Pain rating on the 0-100 VAS from baseline to study endpoint evaluation.

N.B.: The clinical relevance of a 30% change in VAS score is explained and supported in the STATISTICAL ANALYSIS PLAN section further along in this protocol document.

- Overall study success criteria of at least a 35% difference between the test device group and the placebo group, comparing the proportion of individual successes in each group.
- It is anticipated that about 55% of subjects in the test device group and about 20% of subjects in the placebo group will meet the individual success criteria, and
- intended application of a two-tailed test with an alpha value of 0.05 and Power of 0.8

...the sample size of 29 subjects per group (test group and the control group, separately) has been determined using the following reference calculator:

Hypothesis Testing: Categorical Data - Estimation of Sample Size and Power for Comparing Two Binomial Proportions in Bernard Rosner's *Fundamentals of Biostatistics*.

For the purposes of sample size calculation, it is anticipated that about one-twentieth of subjects overall may withdraw from the study prior to completion for various reasons. Therefore, the following formula is used to determine the final needed starting sample size for each group:

Final sample size = sample size X $1/(1-d)$; where d = # expected dropouts/# subjects enrolled.

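### The protocol names two different sole holders of the A/B code and two different assigning parties, and its open-label section gives an unblinding trigger that does not match the blinding sections

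*Combined protocol and SAP*

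**What the plan says.** **Custody of the code.** Double Blind Design, item 1: "Only the study Sponsor will know which label" is the active device, with the information kept at the Sponsor's premises. Randomization: "only the Investigational Device Engineer will know which assignment (A or B) corresponds to the active device", followed by "The Engineer will not reveal this information to any source (investigators, subjects, CRO, or Sponsor" until the final analysis is done and the open-label phase starts.

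**Assignment.** Double Blind Design, item 1: "Each subject will be randomly assigned to Procedure Group A or to Procedure Group B by the independent study Monitor". The Monitor entry under Study Information reads "Erchonia Corporation", which is also the Sponsor. The last paragraph of Randomization instead has the Principal Investigator contact the Sponsor, who issues assignments in sequence as the central source.

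**Release of the code.** Double Blind Design keeps subject and investigator blind "until after the study is completed" and says of the code: "This knowledge will not be shared with the investigators, the subjects, or the study Monitor until the final data analysis is complete". Randomization ties release to completion of the final analysis and the start of the open-label phase. The Open-Label Placebo Subject Procedure Administration Period section breaks blinding for individual subjects once the three-month phase is complete, and does not mention the analysis.

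**Who sees the letter.** Double Blind Design, item 3, limits each subject's letter to the administration investigator and withholds it from the assessment investigator, who records outcomes. Randomization has the Principal Investigator request the assignment. The VAS entry in Study Test Battery makes the Principal Investigator solely responsible for measuring and recording the VAS.

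**The concern.** The primary endpoint is a responder rate on a self-reported pain VAS, and the results are meant to support a 510(k) submission. The claim therefore depends on showing who was blind, and until when. As written, a reader cannot tell whether the party issuing assignments knew which letter was active, or which event releases the code.

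The release rule matters more than usual because there are only two fixed labels. The administration investigator knows every subject's letter at the site, so one early reveal would decode all remaining subjects for that person. The protocol's heading promise, "Maintenance of study double-blind throughout the entire course of the study", would then fail for that member of staff.

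The VAS measurement adds a smaller question: whether the person who requests the assignment, and who also measures the VAS line, learns the letter.

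**Working it through.** The plan gives no figure on this point, so there is none to reproduce. The check compares the sections and then counts what each reading would expose.

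**1. Custody and assignment (no accrual assumption needed).** There are two stated key-holders (Sponsor in Double Blind Design, Engineer in Randomization) and two stated assigners (Monitor in Double Blind Design, Sponsor in Randomization), giving 2 × 2 = 4 combinations.

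| Holds code | Issues assignments | Consequence |
|---|---|---|
| Sponsor | Sponsor | One party knows the arm of all 64 subjects as it issues them |
| Sponsor | Monitor | Different roles, same company according to Study Information |
| Engineer | Monitor | Issuer does not hold the code |
| Engineer | Sponsor | Issuer does not hold the code |

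Treating the Engineer as part of the Sponsor does not remove the conflict, because Randomization names the Sponsor among those not told. The tally counts readings; it is not a probability.

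**2. Timing.** Inputs: 64 subjects (Sample size); a 6-week procedure phase with the primary rating at its end (Procedure Administration Protocol; Evaluation Time Point); follow-up of 3 months, about 12 weeks (Post-Procedure Evaluation Phase).

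*Single reveal after the final analysis:* every primary rating precedes release, so 0 of 64 are exposed at any accrual length.

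*Rolling reveal, subject by subject:* assume uniform starts over T weeks (T is not stated) and follow-up of F weeks. The first subject is unblinded at week 6 + F. A subject starting at week s gives the primary rating at week s + 6, which falls after that reveal when s > F. The share exposed is therefore max(0, (T − F)/T).

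| T (weeks, assumed) | F = 12: share, of 64 | F = 13: share, of 64 |
|---|---|---|
| 12 | 0, 0 | 0, 0 |
| 18 | 6/18 = 0.333, about 21 | 5/18 = 0.278, about 18 |
| 26 | 14/26 = 0.538, about 34 | 13/26 = 0.500, 32 |
| 52 | 40/52 = 0.769, about 49 | 39/52 = 0.750, 48 |

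If a reveal at one site does not reach the other, the same formula applies within each site.

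**3. Meaning of the final analysis.** Secondary Efficacy Outcome Measures lists data sets 2 to 5, all of which use open-label data from former placebo subjects. Randomization requires the final analysis to be complete before release, but these data are collected only after release. The final analysis in Randomization therefore cannot include data sets 2 to 5, and the protocol does not say what it does include.

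**4. VAS measurer.** The Principal Investigator requests the assignment and measures the VAS, while item 3 of Double Blind Design bars the outcome recorder from knowing the letter. Randomization does not say to whom the letter is returned. These statements are in tension, but they do not contradict each other outright.

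**The case against.** The custody conflict cannot be read away. The strongest objections concern the rest.

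- **Timing.** The open-label section can be read together with Randomization, so that both conditions must be met before release. The study-completion wording and the post-study label on the open-label period support a single reveal. This stands: a single reveal is the better-supported reading, and the exposure counts apply only to the weaker one, under assumed accrual. However, the open-label section speaks of individual blinding and sets no analysis condition, so a site could follow it literally.
- **Limits on harm.** Assignments come in sequence from a computer-generated list, which restricts what a code-aware issuer could do. The subject marks the VAS and is not told the letter, and the administration investigator does not record outcomes. All of this stands, and it is why the finding concerns exposure and not demonstrated bias.
- **Monitor and Engineer.** The word independent may mean independent of the sites, and the Monitor might generate the list while the Sponsor relays it. The protocol says neither. The Engineer's employer is also unstated, so the two Engineer combinations separate the roles but are not shown to separate the organisations.
- **Final analysis.** In context it most naturally means the blinded-phase analysis. That is reasonable, and a definition would settle it.
- **VAS measurer.** Item 3 already states the rule, and measuring a mark the subject has made leaves less room for influence. This limb is a request for clarification.

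**Conclusion.** The protocol is wrong as written on custody and assignment: two sections each name a different sole holder of the code, and they name different assigning parties. One of the four permitted combinations has the issuer of all 64 assignments knowing the arm of each; that conclusion needs no assumption. The unblinding triggers do not match. The consequence is 0 of 64 primary ratings under the better-supported single reveal. Under a rolling reveal with uniform accrual over 12 to 52 weeks, it is 0 to about 49 (0 to 48 if three months is taken as 13 weeks). The size of any resulting bias cannot be computed from the documents, and none is shown. The point should be fixed, with high confidence in the custody and assignment contradictions.

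**What to change.** 1. Name one key-holder who does not issue assignments, and one assigning party. Make Double Blind Design and Randomization agree, and state the employer of each.
2. Use one release rule in Double Blind Design, Randomization and the open-label section: the code is released once, for all subjects, after the last subject's three-month evaluation, lock of the blinded-phase database, and completion of the blinded-phase analysis. Define the final analysis as the primary analysis plus secondary data set 1, with the open-label data sets analysed later. In the same edit, resolve the list of data sets: the section announces four, and the fifth repeats the third.
3. State that the assignment letter goes directly to the administration investigator and not to the person who measures the VAS, and align item 3 of Double Blind Design, Randomization and the VAS entry in Study Test Battery.

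**Cost.** The document change is wording only. Compared with rolling unblinding, a placebo subject starting at week s waits T − s weeks longer for the open-label offer. That is at most T, and T/2 on average under uniform accrual (at an assumed T = 26: up to 26 weeks, mean 13), plus lock and analysis time. Randomization already implies this wait. The open-label section's requirement that subjects continue their abstinence presumes no gap before the open-label period, so it must be reconciled with the chosen release rule.

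### The plan limits the A/B letter to the administration investigator, but its assignment step routes the letter through the Principal Investigator; an enroller who holds past site letters can guess the next about 70% of the time.

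*Combined protocol and SAP*

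**What the plan says.** The RANDOMIZATION section sets variable blocks, with "varying block sizes of two, four and six used at random to minimize the likelihood of predicting the next procedure group assignment", and adds that "randomization will be stratified by test site". Its next paragraph describes computer generation as "insuring that the randomization methodology and the generated allocation sequence is concealed from the investigator and subjects".

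On who may know the letter, DOUBLE BLIND DESIGN item 3 separates two roles. The administration investigator gives the procedures and alone knows whether a subject is in Group A or B. The assessment investigator records outcomes and is not told the letter, so that he or she cannot link letters to results.

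On how the letter is obtained, the RANDOMIZATION section says that after consent "the Principal Investigator will contact the Sponsor (via email or phone) who will act as the central source for providing sequential subject procedure group assignment". No recipient other than the Principal Investigator is named. The Principal Investigator also presents the consent form (SIGNING OF INFORMED CONSENT FORM) and has sole responsibility for measuring and recording the VAS marks (STUDY TEST BATTERY, VAS entry).

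**The concern.** Two statements do not fit the rest of the plan. The method is said to be concealed from the investigator, but the block sizes and stratification are printed in the protocol that investigators work from. And the letter is reserved for the administration investigator, but the assignment step, followed as written, gives it to the person who enrols and who measures the primary outcome.

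The second matters more. In a permuted-block list each block closes with equal numbers of A and B. Someone who sees every letter at one site can therefore keep a running tally and guess whichever letter is behind. If that person also forms a view of which letter is active, the choice of whom to consent, or how to judge eligibility, can follow the guess, knowingly or not. Exclusion criterion 13 rests on the investigator's opinion, so there is room for judgement. The same person would also be measuring the VAS with the letter in hand, which item 3 is meant to prevent.

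**Working it through.** The plan states no prediction rate, so there is no document figure to reproduce.

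**Inputs.** Block sizes 2, 4 and 6 and site stratification: RANDOMIZATION. Total: "There will be 64 qualified subjects enrolled in this clinical study", split 1:1 (32 and 32): Sample size. Two sites are listed under STUDY INFORMATION; 32 subjects per site is an assumption (16 to 64 tried). The probability of drawing each block size is not stated; one third each is assumed, with other weights tried.

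**Step 1: guessing rate within a block.** The rule is to guess the letter that is behind, and toss a coin when tied. Expected correct guesses in a block of size 2m are m + (4^m / C(2m, m) − 1)/2.

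| Block size | Expected correct | Rate |
|---|---|---|
| 2 | 1 + (4/2 − 1)/2 = 1.50 | 75.0% |
| 4 | 2 + (16/6 − 1)/2 = 2.83 | 70.8% |
| 6 | 3 + (64/20 − 1)/2 = 4.10 | 68.3% |
| 8 (for comparison) | 4 + (256/70 − 1)/2 = 5.33 | 66.6% |

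**Step 2: the plan's mix.** With equal weights, (1.50 + 2.83 + 4.10)/(2 + 4 + 6) = 8.43/12 = 70.3% in the long run. Simulation, cutting the last block where enrolment stops, gives 69.5%, 69.9%, 70.0% and 70.1% at 16, 32, 48 and 64 subjects per site. At 32 per site, weights of 1/6, 2/6, 3/6 on sizes 2, 4, 6 give 69.1%; weights of 6/11, 3/11, 2/11 give 71.1%. Someone with no past letters is right 50% of the time.

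**Step 3: what the printed sizes add.** Because each block closes balanced, the site tally equals the tally inside the current block, and the rule needs no knowledge of sizes. A Bayes-optimal guesser who knows the sizes and all past letters scores the same 69.9% at 32 per site. Knowing the sizes only shows which guesses are certain, about 4% of them.

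**Step 4: dropping size two.** Sizes 4 and 6: (2.83 + 4.10)/10 = 69.3% long run, 68.8% simulated at 32 per site. Sizes 4, 6 and 8: 12.26/18 = 68.1% long run, 67.5% simulated. The gain is about 1 to 2 points.

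**Step 5: from letter to treatment.** Let delta be the difference in a prognostic factor between subjects enrolled when the guess is the letter believed active and those enrolled when it is the other. The expected imbalance between letters is (2 × 0.703 − 1) × delta = 0.41 delta. If the belief about the active letter is right with probability q, the expected active-minus-sham imbalance is 0.41 × (2q − 1) × delta.

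| q | Expected imbalance |
|---|---|
| 0.50 | 0 |
| 0.75 | about 0.20 delta |
| 1.00 | 0.41 delta |

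The documents fix neither q nor delta.

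**The case against.** The strongest reply is that the plan already has the safeguard: item 3 says only the administration investigator knows the letter, and the meaning of A and B is withheld from investigators. That the Principal Investigator receives the letter is an inference, since the assignment sentence says who asks and who provides, not who is told. This stands as far as it goes. The point is a conflict between sections, not a stated instruction to give the Principal Investigator the letter. But a safeguard that the operational step does not carry out needs repair.

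Three stronger readings are tempting and not supported.

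- A reader might infer that printing the sizes, including two, causes the 70%. Step 3 shows that it does not. The second letter of a block of two helps as a certainty only if one knows that the block is a two, and sizes vary at random.
- A reader might take 0.41 delta as the bias in the treatment comparison. It applies in full only if the enroller has correctly decoded the letters; at q = 0.5 it is zero.
- A reader might conclude that concealment has failed. The list of concealment measures begins at (ii) in the text available, so an item may have been lost in extraction and cannot be judged.

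One counterweight remains. Two fixed labels serve all subjects, so a single correct inference decodes every subject. BLINDING EFFICACY EVALUATION itself expects assessors to guess allocation well if the treatment works. A person holding both letters and VAS results could therefore have q above 0.5, though the documents give no value.

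**Conclusion.** The concern holds in a limited form. The RANDOMIZATION section contradicts itself on whether the method is concealed, and its assignment step, on its natural reading, conflicts with DOUBLE BLIND DESIGN item 3. If the enroller does receive the letters, the next can be guessed about 70% of the time (69–71% under the weights tried) instead of 50%. That figure assumes complete knowledge of past letters at the site. Any effect on active versus sham depends on q and delta, neither of which can be derived from the plan, so no bias in the trial result is demonstrated. The change is worth making because it closes a route to selection bias and to an unblinded assessor at almost no cost.

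A related ambiguity belongs in the same edit. The TABLE OF SUBJECT EVENTS randomizes at consent, before qualification, whereas SUBJECT GROUP RANDOMIZATION assigns a fully qualified subject. On the former reading the actual letter, not a guess, could be known while eligibility is still open.

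**What to change.** 1. In RANDOMIZATION, state that the Sponsor sends each letter only to the administration investigator, who takes no part in consent, qualification or VAS measurement. The Principal Investigator may request an assignment but is not told it. This takes the enroller's guess from about 70% back to 50%.
2. Reconcile DOUBLE BLIND DESIGN item 3, the assignment sentence and the VAS entry of the STUDY TEST BATTERY on who may hold the letter. Name one sender as well, since DOUBLE BLIND DESIGN item 1 gives the assignment to the study Monitor, and state whether it precedes or follows qualification.
3. Move the block sizes to a restricted randomization file held away from the sites, so that the concealment statement is true. This alone does not lower the 70%.
4. Optionally, drop the size of two, for a gain of about 1 to 2 points.

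The cost of items 1 to 3 is protocol wording and a different recipient for the assignment message. Item 4 needs a regenerated list and gives slightly looser within-site balance if enrolment stops mid-block.
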